1 PROTOCOL SUMMARY

1.1 Synopsis

Title:	Analysis of the immune response to COVID-19 vaccination and outcomes in individuals with and without immune deficiencies and dysregulations
Study Description:	
This prospective cohort study will assess the pre- and post-vaccination immune responses in individuals with select immunodeficiencies and immune dysregulations compared to healthy volunteers who receive a coronavirus disease 2019 (COVID-19) vaccine, as well as any adverse events (AEs) experienced after vaccination. All required study visits for this protocol may be conducted remotely; in-person visits at the NIH are optional. Subjects who have not yet been vaccinated will undergo baseline blood sampling using finger stick microsamplers and/or venous blood draw within 7 days prior to receiving the vaccine. Additional samples will be requested from participants approximately 14-21 days after dose 1 and 21-28 days after dose 2 (if applicable). Optional samples may be collected at 6, 12, and 24 months post-vaccination. If subsequent booster doses are received while a participant is still on study, blood samples will again be requested approximately 28 days after each booster dose, through the 5th Covid-19 vaccine dose received, and then participants may proceed with the optional 6-, 12-, and 24-month follow-up sample collection. Participants who are able to attend in-person visits at NIH will have optional on-site blood draws 1 and 3 days after doses 1 and 2 (as applicable). Research evaluations will include baseline severe acute respiratory syndrome-coronavirus-2 (SARS-CoV-2) antibody titers to the spike (S), nucleocapsid (N), and receptor binding domain (RBD) proteins, to assess pre-vaccination SARS-CoV-2 exposure and evaluate responses to vaccination. Additional immune markers of interest may include presence of autoantibodies, transcriptomic profiling, T-cell receptor (TCR) repertoire, among others. Participants who only submit finger stick home microsamplers at the timepoints listed above will be evaluated for SARS-CoV-2 antibody titers and autoantibodies only. All subjects will be asked at baseline about prior COVID-19 diagnosis, symptoms, and severity, and will be asked additional questions at follow-up timepoints (including after additional booster doses) about vaccine AEs using standardized questionnaires.

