Primary Objective:	To characterize the immune response to COVID-19 vaccination among immunodeficient and immune dysregulated individuals compared to healthy volunteers.
Secondary Objectives:	
• To characterize the COVID-19 vaccine-associated AEs among immunodeficient and immune dysregulated individuals compared to healthy volunteers.
Exploratory Objectives:	
• Assess the relationship between prior SARS-CoV-2 infection and vaccine-induced immune response.• To characterize pre-vaccine COVID-19 disease prevalence and severity among immunodeficient and immune dysregulated individuals.• To assess induction, strength, and durability of T- and B-cell-specific immune responses to SARS-CoV-2 (as measured by frequency and diversity of SARS-CoV-2 specific T and B cell clonotypes and titers of specific antibody responses), and their correlation to the underlying immune deficiency/dysregulation.• To characterize autoantibodies present in immunodeficient and immune dysregulated individuals before and after COVID-19 vaccination.• To assess the incidence of post-vaccination breakthrough SARS-CoV-2 infection and to determine the SARS-CoV-2 virus genomic sequence in such cases.
Primary Endpoint:	Change in S and RBD immunoglobulin G (IgG) antibody titer from baseline to 14-21 days or 21-28 days (depending on vaccine manufacturer and platform) after vaccine dose 1, and 21-28 days after dose 2 and any subsequent doses (depending on vaccine manufacturer and platform).
Secondary Endpoints:	
• Incidence of vaccine-associated AEs experienced by immunodeficient individuals compared to healthy volunteers.
Exploratory Endpoints:	
• Characterization of post-vaccine immune response and AEs in patients with antibody evidence of prior SARS-CoV-2 infection• Pre- and post-vaccination incidence of COVID-19-associated symptoms experienced in individuals with immune deficiency/dysregulation who are positive for SARS-CoV-2 by serology or diagnostic polymerase chain reaction (PCR).• Characterize how various forms of immune deficiency or dysregulation impact generation, strength, and durability of T- and B-cell responses.

- Incidence of autoantibodies pre- and post-COVID-19 vaccination comparing individuals with immune deficiency/dysregulation to healthy volunteers.

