Abbreviations: AE, adverse event; BCR, B cell receptor; CBC, complete blood count; COVID-19, coronavirus disease 2019; DNA, deoxyribonucleic acid; EDTA, ethylenediaminetetraacetic acid; Ig, immunoglobulin; PBMC, peripheral blood mononuclear cell; N, nucleocapsid; RBD, receptor binding domain; RNA, ribonucleic acid; S, spike; SARS-CoV-2, severe acute respiratory syndrome coronavirus 2; TBNK, T, B, and natural killer (cells); TCR, T cell receptor; NP, nasopharyngeal; OP, oropharyngeal; PCR, polymerase chain reaction.

*Baseline sampling and questionnaire can happen on the day of vaccination as long as it is prior to receiving the dose. Participants may enroll after vaccination was already performed. If these individuals do not have current plans for an additional booster dose, previous timepoint samples will not be obtained and they will proceed with the next relevant sampling timepoint. In this situation, if stored blood samples from studies in which subjects are concurrently enrolled are available, they will be used. If stored samples are not available, these samples will be considered waived. If these individuals plan to receive an additional booster vaccination(s), they will be enrolled prior to the booster dose and follow the normal schedule, including a baseline draw prior to the booster.

**The exact timing of these visits will depend upon vaccine manufacturer and platform (as detailed in the Manual of Procedures) but will fall within the ranges indicated. For subjects who decline participation in the optional long-term follow-up visits, study completion will end after the dose 1 or 2 follow-up visit(s), depending on whether the subject received a 1-dose or 2-dose vaccine. Each time a participant receives an additional booster dose while they are still on study, a 21-28-day visit will be performed, and optional long-term follow-up visits will be offered. Samples will be requested from participants as scheduled after each vaccination and booster (+/- 7 days) however samples received outside of the requested windows are acceptable and will be analyzed at the discretion of the PI.

‡ Not all vaccines require a second dose and therefore these follow-up timepoints will be not applicable for participants receiving those vaccines.

^AE questionnaire will be administered after any additional booster dose.

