Participants who are able to come to the NIH will have the additional option to provide blood samples at days 1 and 3 after each vaccination in order to capture immediate vaccine-induced perturbations of immune responses. Samples will be used to study short-term immunological effects of immunization and boosting. If additional booster doses are received, participants will be asked to submit optional blood samples 21-28 days after the booster vaccination(s), through the 5th dose of a COVID-19 vaccine. Samples received outside of that window samples received outside of the requested windows are acceptable and will be analyzed at the discretion of the PI. Additional optional blood samples may be provided at approximately 6, 12, and 24 months after the final vaccination to assess long-term immunological persistence of vaccine-derived antibodies and T-cell responses. Research evaluations on these samples will include baseline and post-vaccine autoantibody levels as well as SARS-CoV-2 antibody titers to the S, N, and RBD proteins. Serology has been validated across fresh serum and dried blood samples collected using microsamplers (see Figure below)⁸. Venous blood draw may be waived if a participant is unable to obtain it at any given timepoint.

[figure not shown]

Figure 1. Quantification of antibody concentration utilizing 4PL sigmoidal model of recombinant antibody spiked into seronegative blood. **A)** Anti-RBD recombinant human antibody (IgG and IgM) was added to whole blood from two seronegative donors, then absorbed to microsamplers and remaining blood was spun down to isolate serum and analyzed on full spike ectodomain trimer (spike) or receptor-binding domain (RBD) ELISA. Data are mean \pm SEM, n = 3, red = microsampler eluate, gray = matched serum. **B)** Direct comparison of absorbance of range of recombinant antibody concentration in serum (y axis) versus microsampler (x axis) blood samples. **C)** Sigmoidal four-parameter logistic (4PL) curve fitting to recombinant antibody dilution series, 95% confidence intervals shown shaded around fit curve, n = 12 replicates per data point, red = Spike IgG, orange = RBD IgG, blue = Spike IgM, purple = RBD IgM. **D)** Quantification of IgG levels in a sample high-incidence population. **E)** Upper limit of quantification at 1:400 dilution of serum into ELISA (1:10 dilution of microsampler eluate), n = 68. From ref⁸

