Additional research evaluations include analysis of the nature, diversity, and frequency of SARS-CoV-2 specific T- and B-cell receptor clonotypes. These evaluations will be used to assess pre-vaccination SARS-CoV-2 exposure and expected response to vaccination. Additional research evaluations may include virus neutralization assays to assess antibody functional response, flow cytometry, and transcriptome and genetic analyses. Comparisons of the immune response will be made among immunodeficiency/dysregulation subtypes and against healthy controls. This will allow characterization of the differences in post-vaccination immune responses and AE presentation.

Subjects will be asked at baseline about prior COVID-19 diagnosis, symptoms, and severity using standardized questionnaires. This will allow us to characterize the different manifestations of COVID-19, potentially including a lack of hyper-inflammatory symptoms associated with severe disease due to dysregulation of the immune response that will be present in many of the study participants. To conduct active screening for post-vaccination COVID-19 infections, participants will be sent optional saliva collection kits to return to the NIH bi-weekly for 6 months, for PCR and genetic sequencing of the virus. Participants whose samples are PCR positive will be asked to submit an additional COVID-19 symptom questionnaire and will be referred for care as needed. Each time a participant receives an additional booster dose while they are still on study (through the 5th COVID-19 vaccine a person receives), they may participate in optional bi-weekly saliva collections for an additional 6-month period. Since this is optional, saliva samples received outside of the requested windows are acceptable and will be analyzed at the discretion of the PI. At follow-up timepoints, participants will be asked about all possible vaccine-related AEs, which will be particularly important given recent information about possible vaccine-induced anaphylaxis.

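### Declining the optional 6-, 12- and 24-month visits closes a participant out before later boosters, although post-booster titers are part of the primary endpoint; the same rule conflicts with the saliva and booster AE provisions

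*Combined protocol and SAP*

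**What the plan says.** The double-asterisk footnote in section 1.2 sets the completion rule: "For subjects who decline participation in the optional long-term follow-up visits, study completion will end after the dose 1 or 2 follow-up visit(s", according to whether the vaccine takes one dose or two. The next sentence makes the booster visit conditional: "Each time a participant receives an additional booster dose while they are still on study, a 21-28-day visit will be performed". The synopsis (section 1.1) has the same condition: "If subsequent booster doses are received while a participant is still on study, blood samples will again be requested approximately 28 days after each booster". The saliva footnote in section 1.2 and the text of section 4.1 apply it to the extra six months of saliva after a booster.

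The primary endpoint (sections 1.1 and 3) is the change in S and RBD IgG titer after dose 1 and "21-28 days after dose 2 and any subsequent doses (depending on vaccine manufacturer and platform".

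Other provisions do not depend on accepting the long-term visits:

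- The caret footnote in section 1.2 has the AE questionnaire follow every additional booster, with no on-study condition.
- Section 4.1 says "participants will be sent optional saliva collection kits to return to the NIH bi-weekly for 6 months". Section 7.2 supplies the kits to all participants, and section 5.7.2 counts 13 saliva collections.
- Section 4.1 treats the booster sample as voluntary: "participants will be asked to submit optional blood samples 21-28 days after the booster vaccination(s), through the 5th dose of a COVID-19 vaccine".
- The single-asterisk footnote in section 1.2, and section 4.1, enrol already-vaccinated people who plan a booster before that booster, with a baseline draw.

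**The concern.** Refusing one set of optional visits removes a participant from other parts of the study that they may be willing to do. The part that matters most is the post-booster titer, because it belongs to the primary endpoint. A participant who would give a booster sample but declines long-term visits is closed out before the sample can be requested.

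Two things are at stake. The first is information: fewer post-booster titers in disease groups that are already small (section 8.2 plans several at 20 to 30, and two at 5 to 10). The second is selection: post-booster data would come partly from people chosen by their willingness to stay. Section 8.4.1 relies on data being missing at random given observed covariates and describes no sensitivity analysis. Breakthrough infection raises a related problem. If some people are watched for weeks and others for six months, a crude proportion mixes risk with length of surveillance, and section 8.4 describes no person-time analysis.

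There is also an operational difficulty. Staff cannot close a participant at the dose 1 or 2 visit and still send that person six months of saliva kits and a questionnaire after each booster.

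**Working it through.** **1. What happens to a participant who declines the long-term visits**

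| Item | Provision | Result after close-out |
|---|---|---|
| Booster sample and visit | Only while on study (1.1, 1.2) | Not collected |
| Post-booster saliva | Only while on study (1.2, 4.1) | Not collected |
| Booster AE questionnaire | After every booster, no condition (1.2) | Contradiction |
| First six months of saliva | Kits to all participants (1.2, 4.1, 7.2) | Contradiction |
| Dose 1 and 2 titers | Collected by the completion visit | Unaffected |

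No passage keeps such a participant on study, and none states a route back in. Post-booster titers therefore come from three sources: people who accept long-term visits, people boosted before close-out, and people who enrol just before a booster.

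**2. Saliva collections after close-out, if the completion rule governs**

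Inputs: 13 collections (section 5.7.2), one every 14 days, so 13 × 14 = 182 days. Completed by day d = whole part of d/14. Nominal visit windows are used, without the ±7-day allowance.

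- Saliva counted from the last primary dose, close-out at day 14 to 28: 1 to 2 completed, 11 to 12 of 13 lost (85–92%).
- Saliva counted from dose 1 of a two-dose series, close-out at day 42 to 56: 3 to 4 completed, 9 to 10 of 13 lost (69–77%). This assumes 21 to 28 days between doses, an interval the documents do not give.

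**3. Precision at a booster timepoint (illustration)**

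Section 8.3 says that 20 per group detects 1.05 SD with 90% power (two-sided two-sample t-test, α = 0.05). With noncentrality d√(n/2) = 1.05 × √10 = 3.32 on 38 degrees of freedom, power is 89.9%. The difference detectable at 90% power is 1.052 SD, so the plan's figure reproduces.

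Now suppose a share of each group declines and is boosted only after close-out. The shares are assumed.

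| Share lost | n per group | Power at 1.05 SD | Detectable at 90% power |
|---|---|---|---|
| 0% | 20 | 89.9% | 1.05 SD |
| 10% | 18 | 86.4% | 1.11 SD |
| 25% | 15 | 79.3% | 1.23 SD |
| 50% | 10 | 60.3% | 1.53 SD |

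**4. Crude breakthrough incidence (illustration)**

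Assumed: a six-month risk of 10% in both groups, constant hazard, and surveillance that stops at close-out for those who decline. Risk seen by close-out is 1 − 0.9^(28/182) = 1.6% at 28 days, or 1 − 0.9^(56/182) = 3.2% at 56 days.

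- 80% v 40% accepting, 28 days: 0.8 × 10 + 0.2 × 1.6 = 8.3% v 0.4 × 10 + 0.6 × 1.6 = 5.0%, ratio 1.7.
- 80% v 40% accepting, 56 days: 8.6% v 5.9%, ratio 1.5.
- 70% v 50% accepting: ratio 1.3 at 28 days and 1.2 at 56 days.

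The true ratio is 1 throughout.

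**The case against.** This is a voluntary, exploratory cohort, and much of the stronger case does not hold.

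- A reader might infer that post-booster data come only from people who accept long-term visits. They do not: section 4.1 brings in people enrolled just before a booster, and a booster before close-out is also covered.
- A reader might infer that the plan stops the first six months of saliva, or restricts booster AE questionnaires to people on study. No passage says either. These are contradictions with the completion rule, not stated restrictions.
- A reader might suppose that people decline because a long-term visit is more burdensome than a booster sample. The schedule lists the same microsampler for both, only one sample type is required off-site, and someone who opts in may stop at any visit they choose.
- A reader might take the ratio of 1.7 as an expected bias. Its inputs are assumed, the endpoint is exploratory, and no patient-control contrast is stated for it.
- Bias in the primary comparison is not shown. The model includes group, timepoint and baseline terms, so unequal opt-in by group does not by itself distort it. Antibody results are returned only after certified confirmatory testing (section 7.4), so choosing on one's own titer is unlikely.

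These points limit the size of the concern. What stands is the close-out itself. Being offered a voluntary booster sample differs from being closed before the offer, and the conflicting passages cannot all be followed.

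**Conclusion.** The concern holds for a defined group: participants who decline the long-term visits and receive a booster after the dose 1 or 2 visit. Followed as written, the rule forgoes their post-booster titers, which the primary endpoint calls for, and their post-booster saliva. It also contradicts the booster AE questionnaire and the six-month saliva provision. If completion governs, 69–92% of the planned saliva collections (9 to 12 of 13) fall after close-out, depending on when collection starts.

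The effect on post-booster comparisons cannot be sized, because the documents give no decline rate and no timing of boosters relative to close-out. The power losses and the incidence ratios of 1.2 to 1.7 show what assumed inputs would do; they are not estimates for this study. The documents do not support a claim that the primary analysis is biased. The change is worth making because it is cheap and keeps data that the primary endpoint needs.

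**What to change.** - Amend the completion footnote so that declining the 6-, 12- and 24-month visits does not end participation. Those who are willing stay on study for booster notification, the 21–28-day booster sample (microsampler accepted), the AE and COVID-19 questionnaires, and saliva if they opted in, for as long as boosters through the fifth dose are followed.
- Reconcile the status of the booster sample. Section 1.2 says the booster visit will take place, while section 4.1 calls the sample optional.
- Compute breakthrough incidence per person-time under surveillance, ending each person's time at the last saliva sample or infection questionnaire.
- Report, by group, how many declined the long-term visits and how many gave a post-booster sample, so that selection can be seen.

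The cost is protocol and consent wording, and more mailed kits and questionnaire links of types already in use. No new procedure or extra participants are needed. Some self-selection will remain, because these samples are voluntary.

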1.2 Schedule of Activities

Evaluation	Study Day (window)							
	Screening and Baseline*	Vaccine dose 1 Follow-up			Vaccine dose 2 Follow-up [‡]			Optional Follow-up [†]
	-7 to 0	1 day after vaccination [§]	3 days after vaccination [§]	14-21 OR 21-28 days after vaccination ^{**}	1 day after vaccination [§]	3 days after vaccination [§]	21-28 days after vaccination ^{**}	6, 12, and 24 months (±2 weeks) after last vaccination
Informed consent	X							
Clinical Procedures and Evaluations								
COVID-19 history and symptom questionnaire	X							
Baseline medical history and screening questionnaire	X							
Changes in medical history questionnaire				X			X	X
Electronic AE questionnaire [^]				X			X	
Behavioral questionnaire							X	
Clinical Laboratory Evaluations ^{^^}								
Blood Volume (mL)								
CBC with differential	3 mL	4 mL	4 mL	3 mL	4 mL	4 mL	3 mL	
TBNK lymphocyte phenotyping/flow/cytok		[X]	[X]		[X]	[X]		

Research Laboratory Evaluations ^{^^}	Blood Volume (mL)							
	0.8 mL	0.8 mL	0.8 mL	0.8 mL	0.8 mL	0.8 mL	0.8 mL	0.8 mL
Mitra microsampler [¶] 
 SARS-CoV-2 antibody (S, RBD, N – IgG, IgM, IgA) Autoantibodies 	0.8 mL			0.8 mL			0.8 mL	0.8 mL
Serum (red cap) ^{††} 
 Neutralizing SARS-CoV-2 antibodies 	5 mL	5 mL	5 mL	5 mL	5 mL	5 mL	5 mL	5 mL
Plasma isolation (EDTA purple cap) [¶] 
 DNA isolation (for high throughput sequencing of TCR/BCR repertoire and for genetic studies) 	10 mL	10 mL	10 mL	10 mL	10 mL	10 mL	10 mL	10 mL
PAXgene tube ^{††} 
 Whole blood RNA 	2.5 mL	2.5 mL	2.5 mL	2.5 mL	2.5 mL	2.5 mL	2.5 mL	2.5 mL
PBMC isolation (sodium heparin green top OR EDTA purple cap) ^{††} 
 Lymphocyte/plasmablast Functional T cells 	10 mL	10 mL	10 mL	10 mL	10 mL	10 mL	10 mL	10 mL
Saliva ^{‡‡} 
 SARS-CoV-2 PCR and sequencing 	Bi-weekly through 6 months							
Daily Blood Volume	31.3 mL	31.5 mL	31.5 mL	31.3 mL	31.5 mL	31.5 mL	31.3 mL	31.3 mL
Cumulative Blood Volume	31.3 mL	62.8 mL	94.3 mL	125.6 mL	157.1 mL	188.6 mL	219.9 mL	251.2 mL (6 mos.) 282.5 mL (12 mos.) 313.8 mL (24 mos.)

[X] = will be performed with portion of sample collected for CBC with differential and does not require additional volume.

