4 STUDY DESIGN

4.1 Overall design

This is a prospective, exploratory, cohort study to evaluate the baseline and post-vaccination immune responses in individuals with select immune deficiencies compared to healthy volunteers who receive a COVID-19 vaccine, as well as any AEs experienced after vaccinations. Due to the ongoing pandemic and limited availability of vaccines at the time of preparation of this protocol, participants will receive vaccine externally (i.e., via private physicians or community resources, and not as study interventions). Study visits may be conducted in person or remotely. If participants cannot attend in-person visits at the NIH CC, they can choose to have blood drawn at a primary care provider, academic hospital laboratory, or Quest Diagnostics, as

necessary, and will be sent sampling kits containing all tubes and instructions for the drawing facility. All participants will also be provided with microsamplers kits and mailing supplies to collect and send in fingerstick samples if they are unable to obtain venous blood samples at an off-site facility. Participants will be asked to provide samples at baseline (collected within 7 days prior to receiving the vaccine), 14-28 days (depending on vaccine manufacturer and platform) after dose 1 and 21-28 days after dose 2 (if applicable). Samples will be requested from participants as scheduled after each vaccination (+/- 7 days) however samples received outside of the requested windows are acceptable and will be analyzed at the discretion of the PI.

Participants may enroll after vaccination was already performed. If these individuals do not have current plans for an additional booster dose, previous timepoint samples will not be obtained and they will proceed with the next relevant sampling timepoint. In this situation, if stored blood samples from studies in which subjects are concurrently enrolled are available, they will be used, otherwise they will be waived. If these individuals plan to receive an additional booster vaccination(s), they will be enrolled prior to the booster dose and follow the normal schedule, including a baseline draw prior to the booster.

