8 STATISTICAL CONSIDERATIONS

8.1 Study Hypotheses

This is an exploratory study to characterize the immune response and vaccine-associated AEs in individuals with a variety of immune disorders who receive COVID-19 vaccination, in addition to describing disease prevalence and severity among subjects previously infected with SARS-CoV-2 and whether this affects vaccine immune response. We therefore hope to generate and test a number of hypotheses, including but not limited to:

1. Assessing whether and which of the immune correlates measured for the primary, secondary and exploratory endpoints change significantly after vaccination from baseline, comparing the response among various immune deficiency/dysregulation conditions and healthy volunteers (longitudinal change in immune response).
2. Assessing whether and which of the immune correlates measured for the primary, secondary, and exploratory end-points are significantly different among various immune disorder subgroups and healthy volunteers (cross-sectional immune response).
3. Assessing whether the dose 1 antibody response is correlated with the dose 2 antibody response among various immune disorder subgroups and healthy volunteers.
4. Assessing the incidence of vaccine-associated AEs among various immune disorder subgroups and healthy volunteers.
5. Assessing the prevalence and severity of COVID-19 symptoms among various immune disorder subgroups and healthy volunteers.

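### Nothing requires the dose 1 follow-up sample to be drawn before dose 2, so a post-dose-2 draw can enter the primary analysis as a dose 1 value

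*Combined protocol and SAP*

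**What the plan says.** The Schedule of Activities (section 1.2) puts the dose 1 follow-up at "14-21 OR 21-28 days after vaccination". Its double-asterisk footnote adds: "Samples will be requested from participants as scheduled after each vaccination and booster (+/- 7 days". Section 4.1 repeats the tolerance: "Samples will be requested from participants as scheduled after each vaccination (+/- 7 days". Both places go on to accept later or earlier draws: "samples received outside of the requested windows are acceptable and will be analyzed at the discretion of the PI".

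The same footnote makes the exact timing depend on the vaccine, "as detailed in the Manual of Procedures) but will fall within the ranges indicated". That manual is not among the documents.

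Order relative to a dose is written down for baseline: "Baseline sampling and questionnaire can happen on the day of vaccination as long as it is prior to receiving the dose". Sections 1.2 and 4.1 also require a draw before the booster for people who enrol ahead of one. There is no matching sentence for the dose 1 follow-up sample and dose 2. The study does not set the date of dose 2, because "participants will receive vaccine externally (i.e., via private physicians or community resources, and not as study interventions".

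The primary endpoint (section 3) includes the change in S and RBD IgG after dose 1. Section 8.4.1 models log antibody with timepoint as a category. It gives no term for actual day or doses received, and no rule for placing a sample at a timepoint. Section 8.1 also plans "Assessing whether the dose 1 antibody response is correlated with the dose 2 antibody response".

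**The concern.** A dose 1 value is meant to measure the response to one dose. If the draw can follow dose 2 and still be labelled dose 1, that timepoint mixes one-dose and two-dose responses.

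This matters for the comparison with healthy volunteers even if late draws are equally common in every group. Section 8.3 expects poor antibody responses in some groups. If healthy volunteers start to rise soon after dose 2 and those patients do not, the same share of late draws lifts the healthy mean more and widens the apparent dose 1 gap. Even with equal shares and equal rises, mixing adds scatter and costs power. The planned dose 1-dose 2 correlation is affected too, because some pairs would then consist of two post-dose-2 values.

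**Working it through.** **1. The plan's own figure.** Section 8.3 gives a day 29 RBD spread of 0.38 (labelled a standard error, but used as an SD) and an example with 20 per group. A two-sided two-sample t-test at alpha 0.05 with SD 0.38 gives power 0.900 for a difference of 0.4 and 0.810 for 0.35. Both match the stated 90% and 80%, so 0.35-0.4 is a fair yardstick.

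**2. Permitted days after dose 2.** Add 7 days to each end of the range:
- 14-21 window: day 7 to day 28, 22 days.
- 21-28 window: day 14 to day 35, 22 days.

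Days after dose 2 = last permitted day minus dose 2 day, or zero if negative. The dose 2 day is an assumption.

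| Window | Assumed dose 2 day | Days after dose 2 |
|---|---|---|
| 14-21 | 21 | 28 - 21 = 7 of 22 (32%) |
| 14-21 | 28 or later | 0 of 22 |
| 21-28 | 28 | 35 - 28 = 7 of 22 (32%) |
| 21-28 | 35 or later | 0 of 22 |

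Without the tolerance, both 7-of-22 cases become 0 of 8, so in those cases the 7 days create the overlap. Section 8.3 gives weak indirect evidence on the interval. It uses day 56 as a nearest available timepoint; if that stands for 21-28 days after dose 2, dose 2 falls on day 28 (56 - 28) to day 35 (56 - 21). That range includes both a 7-day overlap and none.

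**3. Shift in a dose 1 mean.** Let f be the share of dose 1 samples drawn after dose 2 and g the share of the dose 2 rise present at the draw. From the section 8.3 table, the rise from day 29 to day 56 is 5.57 - 4.97 = 0.60 log10 for RBD and 5.89 - 5.04 = 0.85 for S-2P. Shift = f × g × rise. Both f and g are assumptions.
- RBD, f = 5%, g = 0.25: 0.05 × 0.25 × 0.60 = 0.01
- RBD, f = 10%, g = 0.5: 0.03
- RBD, f = 20%, g = 0.5: 0.06
- RBD, f = 32%, g = 1: 0.19 (upper bound)
- S-2P, f = 32%, g = 1: 0.27 (upper bound)

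The bias in the group contrast is the healthy shift minus the patient shift. It equals the figures above only if patients show no early rise.

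**4. Power with equal mixing and equal rise.** The difference stays 0.4 and the SD becomes √(0.38² + f(1-f)(g × 0.60)²). For f = 10%, g = 0.5 the SD is 0.391 and power 0.88. For f = 32%, g = 1 the SD is 0.472 and power 0.74 (upper bound on the loss).

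**5. Correlation.** Let a share f of the dose 1 values equal the dose 2 value. With dose 1 and dose 2 SDs s1 and s2 and true correlation r:
- covariance = (1-f) r s1 s2 + f s2²
- variance of the dose 1 label = (1-f) s1² + f s2² + f(1-f) rise²

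S-2P (s1 = 0.28, s2 = 0.19), r = 0.5:
- f = 10%: 0.02755 / (0.3731 × 0.19) = 0.39
- f = 30%: 0.02945 / (0.4663 × 0.19) = 0.33

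RBD (s1 = 0.38, s2 = 0.27):
- r = 0.5 becomes 0.48 at both 10% and 30%.
- r = 0.3 becomes 0.31 at 10% and 0.36 at 30%.

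So the correlation can move either way.

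**The case against.** The strongest reply is that the overlap is conditional and perhaps small. The dose interval is not in the documents. The Manual of Procedures may name a specific day: day 14 with 7 days either side ends on day 21 and would not overlap a day 21 dose. The schedule lists the dose 1 follow-up ahead of the dose 2 visits, with cumulative blood volume running in that order, so the intended sequence is visible. Section 5.7.2 pays for on-time completion, which pulls draws towards the nominal window. Calendar days are not shares of samples, and a draw within 7 days of dose 2 may show little of its effect. The study describes itself as exploratory.

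All of this limits the size and stands. None of it supplies the missing order rule or an assignment rule, and the open acceptance of out-of-window samples weakens any narrowing by the manual.

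A reader might infer more than the documents support:
- **That dose 2 response is being counted as dose 1 response.** The text only allows it; no passage says such draws will be labelled dose 1.
- **That most permitted days could fall after dose 2.** Pairing the 21-28 window with a day 21 dose gives 14 of 22, but windows are vaccine-specific and nothing supports that pairing.
- **That the dose 1-dose 2 correlation is inflated.** The check shows attenuation for S-2P and either direction for RBD.
- **That the tolerance misattributes adverse events between doses.** The 7 days is written for samples. Section 7.2 times the AE form only as following vaccination, the form itself is not shown, and section 8.4.2 compares incidence by group, not by dose.

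**Conclusion.** The point holds as a gap in the timepoint definition. Following the plan as written, a sample drawn after dose 2 can enter the primary model as a dose 1 value. With dose 2 assumed on day 21 or day 28, matched to the window, and the tolerance added to the whole range, this applies to 7 of 22 permitted days, all within 7 days of dose 2. It applies to none if dose 2 is on day 35 or later. The manual could narrow it; acceptance of out-of-window samples could widen it.

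The effect on the group contrast depends on early dose 2 rises differing between groups. Its size is unknown and probably modest against the plan's 0.35-0.4 example: 0.01-0.06 log10 for RBD under partial-rise assumptions, with 0.19 as a ceiling. It is worth correcting because it affects a primary-endpoint timepoint and the correction is cheap.

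**What to change.** - **Section 1.2 (double-asterisk footnote) and section 4.1:** state that the dose 1 sampling window closes at receipt of dose 2; a draw on the same day is acceptable if taken before the dose. This governs sampling only and does not alter the timing of any vaccine dose.
- **Section 8.4.1:** assign each sample to the last dose received before the draw, using recorded dose and draw dates. A sample drawn after dose 2 is then not a dose 1 value. Keep such samples under a separate label, report how many there are by group, and use them in a sensitivity analysis.
- **Secondary:** have the AE form record the dose and the onset date, if it does not already.

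The cost is a short addition to the schedule and design text, one derivation rule, and some additional missing dose 1 values. The MMRM handles those under missing at random, which section 8.4.1 already assumes.
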